8.2.6. Investigational Product Exposure

Total investigational product exposure (in mg) is defined as the total mg of SAGE-324 that was taken during the study. If a participant skips a dose on any of the days, the dose taken is 0 mg.

Total exposure duration to SAGE-324 (in days) is defined as (date of last dose – date of first dose + 1). Note that this does not exclude days when the dose has been missed.

Planned exposure for participants with no unscheduled dose reductions/increases is defined as the sum of:

- 14 days of treatment (Day 1 through Day 14) times 15 mg
- 14 days of treatment (Day 15 through Day 28) times 30 mg
- 14 days of treatment (Day 29 through Day 42) times 45 mg
- Number of days from Day 43 to end of treatment, inclusive, times 60 mg

If a participant has an unscheduled dose reduction/increase, or dose reductions/increases, planned exposure will be as indicated until the point of the first unscheduled reduction/increase. Planned exposure from the point of the first unscheduled reduction/increase will be the assigned dose times the number of days from the date of the reduction/increase (inclusive) to the date of the next reduction/increase (exclusive) or the date of end of treatment (inclusive). Planned exposure for any additional unscheduled reductions/increases will be handled in a similar manner as the assigned dose times the number of days from the date of the reduction/increase (inclusive) to the date of the next reduction/increase (exclusive) or the date of end of treatment (inclusive).

Percent of the planned exposure received is defined as the total investigational product exposure, divided by planned exposure, times 100.

[figure not shown]
Total investigational product exposure, total exposure duration, and percent of planned exposure received will be summarized using the Safety Set. The number and percentage of participants with percent of planned exposure received <80%, 80% to <100%, and $\geq 100\%$ will be summarized. Total exposure duration (over all doses taken) will also be summarized by dose at time of treatment discontinuation using the Safety Set.

[figure not shown]

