8.2.7. Investigational Product Adherence

[figure not shown]
IP adherence (%) is defined as the number of tablets taken, divided by the number of tablets planned to be taken, times 100. Number of tablets planned to be taken will be derived using an algorithm identical to that used for the derivation of planned exposure, but with the assigned dose replaced with the number of assigned tablets (15 mg = 1 tablet per day, 30 mg = 2 tablets per day, 45 mg = 3 tablets per day, 60 mg = 4 tablets per day).

Total tablets taken and IP adherence will be summarized descriptively using the Safety Set. Number and percentage of participants with IP adherence in categories <75%, 75 to 100%, >100% will be provided.

A large black rectangular redaction box covers the majority of the page content, from approximately y=150 to y=950. In the top left corner, there are four smaller black rectangular redaction boxes: one at the top left, one below it, one to its right, and one below that one. The rest of the page is white.

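### For participants with no unscheduled dose change, SAP planned exposure and planned tablets do not cut the titration blocks at end of treatment, so the percentages are wrong for anyone whose last dose falls before Day 42

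*SAP*

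**What the plan says.** SAP 8.2.6 has two branches.

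**No unscheduled dose change.** The rule opens "Planned exposure for participants with no unscheduled dose reductions/increases is defined as the sum of" and has four terms. The first two charge two weeks at 15 mg, ending on Day 14, and two weeks at 30 mg, ending on Day 28. The third reads "14 days of treatment (Day 29 through Day 42) times 45 mg". The last one covers the maintenance dose and is worded differently: "Number of days from Day 43 to end of treatment, inclusive, times 60 mg". So the three titration terms carry a fixed count of 14 days, and only the maintenance term refers to end of treatment.

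**Unscheduled reduction or increase.** Here "planned exposure will be as indicated until the point of the first unscheduled reduction/increase". After that change, the plan is the assigned dose for each day, counted "to the date of the next reduction/increase (exclusive) or the date of end of treatment (inclusive".

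SAP 8.2.7 extends the rule to adherence: "Number of tablets planned to be taken will be derived using an algorithm identical to that used for the derivation of planned exposure". One to four tablets per day then stand in for the dose.

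Both percentages divide the amount taken by the amount planned. Exposure is grouped as below 80%, 80% to below 100%, and 100% or more. Adherence is grouped as below 75%, 75 to 100%, and above 100%. Both are summarized on the Safety Set, which needs only one dose (SAP 7.2), so participants who stop during titration are included.

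**The concern.** A participant who stops during titration without a prior dose change falls in the first branch, and nothing there shortens the titration blocks. The denominator then covers days after treatment ended. A participant reduced during titration who stops on the same day is handled differently, because the second branch ends at end of treatment.

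The affected group is foreseeable. The protocol uses titration to mitigate somnolence (Protocol 5.1, 5.2), and dose reduction is at the investigator's discretion (Protocol 7.4). On Days 1 to 14 the scheduled dose is 15 mg and the decrement is 15 mg, so no lower dose exists and a stop in that period belongs to the first branch.

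What is at stake is whether the exposure and adherence percentages mean what their labels say. Someone who took every tablet up to the day of stopping should score 100%.

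**Working it through.** The SAP states no worked total, so there is no figure of its own to reproduce. The check applies its definitions to a participant who takes every scheduled dose and has no dose change.

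**Inputs.** Day ranges and doses come from SAP 8.2.6; tablets per day come from SAP 8.2.7. End of treatment is taken to be the day of last dose, L. That is an assumption, since 8.2.6 does not define the date.

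**Titration blocks.** 14 × 15 + 14 × 30 + 14 × 45 = 210 + 420 + 630 = 1260 mg. In tablets: 14 + 28 + 42 = 84.

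**Tablets taken by Day L.** L for L ≤ 14; 14 + 2(L − 14) for Days 15 to 28; 42 + 3(L − 28) for Days 29 to 42. Multiply by 15 for mg.

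**Planned amount for L ≤ 42, two readings.**

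- Zero reading: the 60 mg term is 0 before Day 43, so planned = 1260 mg.
- Literal reading: days from Day 43 to Day L inclusive = L − 43 + 1 = L − 42, so planned = 1260 + 60(L − 42) mg.

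Every tablet is 15 mg, so the exposure and adherence percentages coincide.

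| Last dose (day) | Taken, mg (tablets) | Zero reading, % of 1260 mg | Literal reading, planned mg | Literal reading, % |
|---|---|---|---|---|
| 14 | 210 (14) | 16.7 | -420 | -50.0 |
| 20 | 390 (26) | 31.0 | -60 | -650.0 |
| 21 | 420 (28) | 33.3 | 0 | undefined |
| 28 | 630 (42) | 50.0 | 420 | 150.0 |
| 34 | 900 (60) | 71.4 | 780 | 115.4 |
| 35 | 945 (63) | 75.0 | 840 | 112.5 |
| 36 | 990 (66) | 78.6 | 900 | 110.0 |
| 37 | 1035 (69) | 82.1 | 960 | 107.8 |
| 42 | 1260 (84) | 100.0 | 1260 | 100.0 |

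For example, on Day 20 the literal term is (20 − 42) × 60 = −1320 mg, and 1260 − 1320 = −60 mg.

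**Categories under the zero reading.** Last dose by Day 34 falls in below-75% adherence, and Days 35 to 41 stay in 75 to 100%. Last dose by Day 36 falls in below-80% exposure, and Days 37 to 41 in 80% to below 100%.

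**Dose-change branch, for comparison.** Take 15 mg on Days 1 to 14, 30 mg on Days 15 to 19, 15 mg from Day 20 and a stop on Day 25, leaving the interruption before the reduced dose out of this illustration. Planned = 210 + 5 × 30 + 6 × 15 = 450 mg, not 1260 mg.

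**With every term cut at Day L.** Planned equals taken (210 mg at Day 14, 390 mg at Day 20, 630 mg at Day 28), so the percentage is 100% at every stopping day.

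**The case against.** The strongest reply is that truncation was plainly intended. The titration terms count days of treatment, and someone who has stopped has none left. The 60 mg term and the whole dose-change branch end at end of treatment, and a negative or zero denominator would be noticed in programming. As to intent, this is persuasive. It does not rescue the text, which gives a fixed count of 14 and makes the programmer either follow it or supply an unwritten rule.

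A reader might infer more than the documents support, in four ways:

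- **That everyone who stops during titration is charged the full 1260 mg.** Not so: a participant with a dose change during titration is counted only to end of treatment, and Protocol 7.4 allows reductions in that period.
- **That compliant early stoppers are bound to appear under-exposed.** That direction needs the 60 mg term to be zero, which the SAP does not say. Read literally, a Day 28 stop appears over-exposed.
- **That all of them would be classed in the lowest adherence group.** Even under the zero reading, last doses on Days 35 to 41 remain in 75 to 100%.
- **That the tolerability result would be distorted.** Tolerability is assessed from TEAEs and the other safety data (SAP 8.4). Early exits are reported directly: discontinuation by dose level and reason (8.2.1), TEAEs leading to discontinuation (8.4.1), and exposure duration by dose at discontinuation (8.2.6). None of these uses planned exposure.

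**Conclusion.** The defect is real and narrow. For a fully compliant participant with no unscheduled dose change whose last dose is before Day 42, neither reading of SAP 8.2.6 gives the correct 100%. The error can be large for an individual, and its direction depends on a choice the SAP leaves open.

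It reaches only the percent-of-planned-exposure rows of Table 14.1.8.1, the adherence rows of Table 14.1.8.3 and the related listing (16.2.5.3). The primary endpoint, total mg taken, exposure duration and disposition do not depend on it. The effect on the tables as a whole cannot be sized: the documents give no rate of discontinuation during titration, and entry requires completing treatment in an earlier SAGE-324 study (Protocol 8.1, criterion 5), which may limit early exits.

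The per-participant figures assume perfect intake to the last dose and end of treatment on that day. It should be corrected, because a stated rule yields wrong values and the repair is simple.

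**What to change.** Add one sentence to SAP 8.2.6: for participants with no unscheduled dose change, each of the four terms counts only days from Day 1 up to and including the date of end of treatment, and any term that would start after that date is zero. Use the same end-of-treatment date as the dose-change branch, and say which date that is. Leave that branch's assigned-dose rule as it stands, so that the scheduled titration doses do not override an assigned reduced dose. State in 8.2.7 that planned tablets follow the same rule.

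The cost is a short SAP edit and a small programming change, with no protocol amendment and no new data. If the database is already locked, SAP section 2 provides for documenting the change in the clinical study report.

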7.4. Dose Adjustment Criteria

If a participant experiences AEs at any time during the Treatment Period that are considered by the investigator to be related to the IP and not tolerable, the investigator may reduce the dose of

IP in 15 mg decrements, including during the initial dose escalation period. Administration of IP will be interrupted for 3 to 8 days before the initiation of the reduced dose.

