8.4.1. Adverse Events

Adverse events will be coded using MedDRA Version 25 or higher. In the event of a missing/incomplete start or stop date associated with an adverse event, only the treatment-emergence will be imputed using the algorithm described in [Appendix B](#). Dates will not be imputed.

A TEAE is defined as an AE with onset at or after the first dose of IP (SAGE-324). Summary tables of AEs will include TEAEs only and will summarize data using the Safety Set participants overall and by dose level taken immediately prior to the AE onset.

An overall adverse event summary table will be presented for TEAEs and will include the number and percent of participants experiencing at least one:

- TEAE
- Maximum severity of TEAE (mild TEAE, moderate TEAE, severe TEAE)

- TEAE leading to dose interruption
- TEAE leading to dose reduction
- TEAE related to IP
- TEAE leading to IP discontinuation
- TEAE leading to study discontinuation
- Serious TEAE
- Serious TEAE related to IP
- Serious TEAE leading to IP discontinuation
- Serious TEAE leading to study discontinuation
- TEAE resulting in death

The incidence of TEAEs will be summarized by System Organ Class (SOC) and Preferred Term (PT). In addition, summaries will be provided by maximum severity (mild < moderate < severe) and by maximum relationship (related > not related) to IP. Any TEAEs leading to IP discontinuation, any TEAE leading to study discontinuation, and any treatment-emergent SAEs will also be summarized, sorted by descending frequency in SOC and PT.

Participants will be counted only once within each SOC and PT at the maximum severity in the following order: severe, moderate, and mild. Participants will be counted only once within each SOC and PT at the strongest relationship to IP in the following order: related, not related to IP. An AE with missing severity will be considered as 'severe', and with missing relationship to IP will be considered as 'related' for the purposes of summarizing these data.

The incidence of TEAEs and treatment-emergent SAEs will also be presented in order of decreasing frequency by PT.

All AEs (including those with onset before the start of IP) through the end of the study will be listed. In addition, separate listings containing individual participant AE data for all deaths, SAEs, AEs leading to IP discontinuation, and AEs leading to study discontinuation will be provided.

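### The SAP's planned-exposure and adherence rules count the protocol-required interruption before a dose reduction as missed drug, so a participant who follows the protocol exactly scores below 100%

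*SAP*

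**What the plan says.** Protocol 7.4 allows reductions in 15 mg steps for intolerable related events and states: "Administration of IP will be interrupted for 3 to 8 days before the initiation of the reduced dose". SAP 5.1 repeats this.

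SAP 8.2.6 defines the percent of planned exposure received as mg taken over mg planned.
- **Numerator:** "If a participant skips a dose on any of the days, the dose taken is 0 mg".
- **Denominator, no reduction:** the titration schedule for Days 1 to 42, then "Number of days from Day 43 to end of treatment, inclusive, times 60 mg".
- **Denominator, with a reduction:** "planned exposure will be as indicated until the point of the first unscheduled reduction/increase". From the date of the reduction it is the assigned dose times all days until the next change or the end of treatment.

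Results are reported in bands of <80%, 80% to <100% and ≥100%.

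SAP 8.2.7 defines adherence as tablets taken over tablets planned: "Number of tablets planned to be taken will be derived using an algorithm identical to that used for the derivation of planned exposure". It lists assigned tablets as 1, 2, 3 or 4 per day, with no zero level. The adherence bands are <75%, 75 to 100% and >100%.

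Neither section mentions the interruption, and neither says whether the date of the reduction is the first interrupted day or the first day of the lower dose.

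**The concern.** The denominator builds up on every calendar day, including days on which the protocol tells the participant to take nothing. The numerator is zero on those days. Drug withheld by protocol is therefore scored in the same way as drug forgotten or refused.

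This matters because tolerability is part of the primary objective and reductions are foreseeable: Protocol 5.2 reports that some events in Study 324-ETD-201 required dose reduction or discontinuation. The relative effect is largest in participants who reduce early and stop soon afterwards. In the summary tables their shortfall cannot be told apart from skipped doses. In addition, because the date of the reduction is undefined, two programmers could produce different percentages from the same data.

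**Working it through.** The documents state no adherence or exposure result, so there is no figure to reproduce. The check applies the SAP rule day by day to a participant who takes every dose due and observes the interruption exactly.

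**Inputs.** From SAP 8.2.6: 15, 30 and 45 mg for 14 days each, which is 14 × (15 + 30 + 45) = 1260 mg by Day 42, then 60 mg daily. From Protocol 7.4: an interruption of 3 to 8 days and steps of 15 mg. One tablet is 15 mg, so the mg and tablet percentages are identical. The timing of reductions and of stopping is assumed, because the documents do not give it.

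**General result.** Let T be the mg taken, and let each of k interruption days carry planned dose d. Then percent = 100 × T / (T + k × d). This is below 100 whenever d > 0.
- Reading A (date = first reduced dose): d is the old dose.
- Reading B (date = first interrupted day): d is the reduced dose.

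**Three illustrative participants**
- (a) On 30 mg, interrupted from Day 20, then 15 mg, stops Day 35.
- (b) On 60 mg, interrupted from Day 50, then 45 mg, stops Day 60.
- (c) On 60 mg, interrupted from Day 45, then 45 mg; interrupted from Day 67, then 30 mg; stops Day 90.

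Worked in full for (a), 8 days:
- Taken: 14×15 + 5×30 + 8×15 = 480.
- Planned, Reading A: 14×15 + 13×30 + 8×15 = 720.
- Planned, Reading B: 14×15 + 5×30 + 16×15 = 600.

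| Case | Interruption | Taken (mg) | Planned A (mg) | % A | Planned B (mg) | % B |
|---|---|---|---|---|---|---|
| (a) | 8 days | 480 | 720 | 66.7 | 600 | 80.0 |
| (a) | 3 days | 555 | 645 | 86.0 | 600 | 92.5 |
| (b) | 8 days | 1815 | 2295 | 79.1 | 2175 | 83.4 |
| (b) | 3 days | 2040 | 2220 | 91.9 | 2175 | 93.8 |
| (c) | 8 days, twice | 2490 | 3330 | 74.8 | 3090 | 80.6 |
| (c) | 3 days, twice | 2865 | 3180 | 90.1 | 3090 | 92.7 |

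Only (a) and (c), with 8-day interruptions under Reading A, fall below 75% adherence. All three 8-day cases fall below 80% of planned exposure under Reading A; none does under Reading B.

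**Longer treatment, one 8-day interruption from 60 mg**
- From Day 50, ending Day 365: A 15540/16020 = 97.0%; B 15540/15900 = 97.7%.
- From Day 57, ending Day 365: A 15645/16125 = 97.0%; B 15645/16005 = 97.8%.
- From Day 57, ending Day 1825: A 81345/81825 = 99.4%, still below 100%.

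**How long a low band lasts**
- One 8-day interruption from Day 18 (30 to 15 mg). Under A, 75% is reached only if treatment lasts to Day 53 (720/960) and 80% at Day 69 (960/1200). Under B, 75% is reached at Day 29 (360/480), three days after the restart on Day 26.
- Two 8-day interruptions, from Days 46 and 60. Under A, 75% is reached at Day 94 (2520/3360). Under B, it is reached at Day 70 (1800/2400), two days after the second restart.

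With 0 mg and 0 tablets planned on interruption days, every case gives exactly 100%.

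**The case against.** - **An assigned dose of 0 mg.** The SAP does not define the assigned dose, and a programmer could enter zero during the interruption, which would remove the effect. The text does not exclude this, but it does not direct it either: the rule switches only at a reduction or increase, and the tablet levels start at 1. SAP 8.4.1 lists "TEAE leading to dose interruption" apart from dose reduction, but those are adverse-event rows and only weak evidence about planned exposure.
- **Dose intensity.** For percent of planned exposure, counting interruption days as a shortfall is defensible, and SAP 8.2.6 deliberately keeps missed days in exposure duration. This stands. The criticism has most force for adherence, which should show whether drug was taken as directed.
- **Fully compliant participants are classed as non-adherent.** A reader might infer this, but the SAP defines no such class. Example (b), and every longer-treatment case shown, stays in the 75 to 100% adherence band, the same band as a perfect score.
- **The percentages show reductions instead of compliance.** A reader might infer this too. It goes too far, because tablets genuinely missed still lower both percentages.
- **Other outputs.** SAP 8.4.1 summarises events leading to interruption, reduction and discontinuation. Appendix C lists diary, dosing-log and adherence data by participant. Tolerability is therefore not read from these percentages alone.

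**Conclusion.** The point holds as a flaw in the written rule. Under either reading of the date of the reduction, a participant who follows the protocol exactly and has a reduction scores below 100% adherence and cannot enter the ≥100% planned-exposure band, however long treatment lasts.

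The size is a range: 66.7% to 92.5% in (a), 79.1% to 93.8% in (b), 74.8% to 92.7% in (c), and about 97% to 98% by Day 365 after one 8-day interruption near Day 50 to 57. Falling below 75% adherence needs long or repeated interruptions and early stopping, with the date read as the first reduced dose. Under the other reading it happens only when treatment stops within days of a restart.

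These figures rest on assumed timings. The documents give no rate of reduction or early stopping, so the number of participants affected cannot be stated. Only the descriptive exposure and adherence tables change; the primary endpoint, incidence of TEAEs, does not use them.

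**What to change.** 1. In SAP 8.2.6, define the date of the reduction: either the first interrupted day or the first day of the reduced dose.
2. In SAP 8.2.7, state that protocol-directed interruption days before a reduced dose (Protocol 7.4), from the first interrupted day to the day before the reduced dose starts, contribute 0 planned tablets.
3. In SAP 8.2.6, do the same for planned mg, or label percent of planned exposure as a dose-intensity measure that includes interruption days.
4. Summarise the number of interruption days separately.

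The cost is a few SAP sentences and a small amount of programming. The daily diary and dosing log are already listed in Appendix C, so no new data collection appears necessary. No dosing rule changes.

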5.1. Dose Justification

The present study (324-ETD-303) is a long-term, open-label study to evaluate the safety and tolerability of SAGE-324 in participants with ET. The dose selected for the study is the highest dose that is included in the dose-ranging study 324-ETD-202. Once the dose-ranging study is completed and a dose or doses are selected for inclusion in pivotal studies, this protocol will be amended to employ the highest of the doses included in the pivotal studies. This is in line with the ICH E1A guideline, requiring exposure at the dosage level(s) intended for clinical use.

In order to mitigate the adverse event (AE) of somnolence that was observed in study 324-ETD-201, nighttime dosing will be employed as well as an up-titration to the 60-mg dose (Section 7.3). Up-titration is a standard practice that is designed to allow participants to accommodate to the AE as plasma concentrations rise more slowly than they would if the target dose was administered from the start. Participants will be allowed to down-titrate at any time if intolerable AEs occur.

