7.3. Treatment Assignment

SAGE-324 will be self-administered orally once daily in the evening before bed, with a snack if bedtime is not within 2 hours of the evening meal.

Participants will self-administer 15 mg SAGE-324 on Day 1 to Day 14, 30 mg on Day 15 to Day 28, 45 mg on Day 29 to Day 42, and then 60 mg daily starting on Day 43.

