13.4. Sample Size

The planned sample size is approximately 750 participants to be enrolled and dosed to contribute exposures to the safety database for SAGE-324 in accordance with ICH E1A guidelines.

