5.2. Sample Size and Power

The planned sample size is approximately 750 participants to be dosed and complete the study to contribute exposures to the safety database for SAGE-324 in accordance with ICH E1A guidelines.

[REDACTED]

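### The only planned exposure summary by dose groups each participant's whole time on drug under the dose at discontinuation, so it cannot show exposure at 60 mg; a table by dose actually taken should be added

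*SAP*

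**What the plan says.** Protocol 13.4 gives the sample size as "approximately 750 participants to be enrolled and dosed to contribute exposures to the safety database for SAGE-324 in accordance with ICH E1A guidelines". SAP 5.2 gives the same purpose: "to contribute exposures to the safety database for SAGE-324 in accordance with ICH E1A guidelines". Text next to some of the sample size statements is redacted, so this is the visible rationale only. Protocol 5.1 says of the dose choice: "This is in line with the ICH E1A guideline, requiring exposure at the dosage level(s) intended for clinical use".

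Under Protocol 7.3, participants take 15 mg and then 30 mg for 14 days each, followed by "45 mg on Day 29 to Day 42, and then 60 mg daily starting on Day 43". Protocol 7.4 lets the investigator lower "IP in 15 mg decrements, including during the initial dose escalation period" for related adverse events that are not tolerable, with 3 to 8 days off drug before the lower dose starts.

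SAP 8.2.6 defines exposure duration as last dose date minus first dose date plus 1, and adds: "Note that this does not exclude days when the dose has been missed". Its one split by dose is: "Total exposure duration (over all doses taken) will also be summarized by dose at time of treatment discontinuation using the Safety Set". In Appendix C this is Table 14.1.8.2. The neighbouring tables are 14.1.8.1 (exposure) and 14.1.8.3 (adherence), and neither title carries a dose split. Under SAP 8.1, displays with no evaluation or onset date are shown for the aggregate SAGE-324 group. SAP 8.1 and 8.4.1 assign each adverse event to the dose in force just before it began.

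**The concern.** If the study exists to supply exposure at the intended dose, its report should say how many participants were exposed at 60 mg and for how long. No visible table does so. The planned one answers a different question: how long participants had been on drug in total, grouped by the dose on which they stopped.

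That grouping departs from time at dose in two ways. Those who end on 60 mg bring their titration days with them. Those who end on a reduced dose take all their 60 mg days to the lower group. A reader who sets the by-dose adverse event tables beside this table would then compare quantities built on different rules. For example, a participant with an intolerable event on 60 mg who is reduced and later stops has the event under 60 mg and all the exposure time under the lower dose.

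**Working it through.** The plan gives no required count at any duration, no rate and no precision target, so 750 can be neither reproduced nor refuted. The check is day counting on the SAP's own definitions.

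**Inputs.** Titration is 3 × 14 = 42 days, with 60 mg from Day 43 (Protocol 7.3). The interruption before a reduced dose is 3 to 8 days (Protocol 7.4). Duration is last dose date − first dose date + 1, across all doses (SAP 8.2.6). Two assumptions are needed: every participant is classed by last dose, and there are no missed days beyond the interruption.

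**Participant who ends on 60 mg on Day T.** Duration in the table = T. Days at 60 mg = T − 42. Titration share = 42/T.

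| Last dose on Day | Duration in table | Days at 60 mg | Titration share |
|---|---|---|---|
| 168 | 168 | 126 | 25.0% |
| 365 | 365 | 323 | 11.5% |
| 1095 | 1095 | 1053 | 3.8% |

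A full 182 or 365 days at 60 mg therefore needs a total duration of 182 + 42 = 224 or 365 + 42 = 407 days. If all 750 ended on 60 mg, that group would include 750 × 42 = 31,500 titration person-days, or 31,500/365.25 = 86.2 person-years.

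**Participant reduced before stopping (hypothetical).** Last 60 mg day is Day 335, then the interruption, then 45 mg to Day 365.
- Table: 365 days under 45 mg, none under 60 mg.
- Actual days at 60 mg: 335 − 42 = 293.
- Actual days at 45 mg: 14 in titration plus 365 − 335 − 8 = 22 to 365 − 335 − 3 = 27, so 36 to 41.

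**Cohort illustration (assumed values).** Take 750 participants with 365 days each. A share q ends on 45 mg, with a last 60 mg day of L.
- 60 mg group in the table: 750 × (1 − q) × 365 / 365.25 person-years.
- Actual at 60 mg: 750 × [(1 − q) × 323 + q × (L − 42)] / 365.25 person-years.

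| q | Table | Actual, L = 90 / 182 / 335 | Ratio, table to actual |
|---|---|---|---|
| 0 | 749 | 663 (no reductions) | 1.13 |
| 20% | 600 | 550 / 588 / 651 | 1.09 / 1.02 / 0.92 |
| 40% | 450 | 437 / 513 / 639 | 1.03 / 0.88 / 0.70 |

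The ratio falls on both sides of 1. Without dose-by-day data, the table cannot be converted to exposure at 60 mg.

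**The case against.** The table is openly labelled as total duration over all doses, grouped by dose at discontinuation. It does not claim that those days were spent at that dose, and time on drug by final dose is a legitimate display. This stands: the label is not wrong, and the point is what the plan leaves out.

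Other tables give partial information. By-visit summaries are split by the last dose before the assessment and report n. Vital signs and the Epworth scale are scheduled at Week 24, Month 12 and every 3 months to Month 60, so the number assessed on 60 mg at each visit will be known. That is useful, but it is not cumulative time at 60 mg. Missed doses are disclosed, and they enter total mg taken, percent of planned exposure and adherence. Duration gets the full set of continuous statistics in SAP 8.1 (n, mean, SD, median, quartiles, range), though no count reaching a given duration.

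The primary endpoint is also unharmed. TEAEs go to the dose just before onset, and no visible analysis uses Table 14.1.8.2 as a denominator.

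A reader might infer that the table systematically strips time from 60 mg, or that the study cannot report what it set out to deliver. The documents support neither. The net difference can have either sign, and the plan lists the daily dosing diary and dosing log. The 750 are to contribute to a wider safety database, and the intended-dose wording comes from the dose justification, not from the sample size sections. Protocol 5.1 also foresees an amendment once doses are chosen for the pivotal studies, so 60 mg is the highest dose under study rather than a settled clinical dose. That last point makes days at every level more useful, not less.

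**Conclusion.** The concern holds as a gap in planned reporting. Followed as written, SAP 8.2.6 yields a by-dose exposure summary that cannot show exposure at 60 mg and that assigns dose differently from the adverse event tables. No visible table gives days at each dose taken, or counts participants reaching any duration.

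For a participant ending on 60 mg, the effect is 42 days, which matters for early stoppers and little after several years. For one ending on a reduced dose, it is all of the 60 mg time. In the illustration, the table's 60 mg person-years run from 0.70 to 1.13 times the actual figure. That range rests on assumed reduction shares and timing, one year of follow-up and grouping by last dose. The last assumption is needed because SAP 8.2.1 separates completing from discontinuing treatment, while SAP 8.2.6 does not say where completers go.

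Nothing here shows that 750 is the wrong number or that the primary analysis is biased. This is a cheap improvement.

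**What to change.** Before database lock, add to SAP 8.2.6 and Appendix C an exposure table by dose actually taken, derived from the daily dosing diary and dosing log (Listings 16.2.5.2.1 and 16.2.5.2.2). It should give:

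- days dosed at each level per participant, with undosed days excluded;
- person-time at each level, so that exposure and adverse events are both tied to the dose in use;
- number and percentage of participants reaching stated durations, overall and at 60 mg. Six and 12 months and longer are suggestions; the documents give no cut-offs, so the sponsor should state those it needs.

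Keep Table 14.1.8.2 as a supplementary display and state how treatment completers are classed in it.

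The cost is a paragraph of SAP text and one more table, with no new data collection. Stated exposure may come out slightly smaller once undosed days are dropped.
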